### B. Ultrasound Imaging based Tremor Frequency Prediction

Hypothesis: Tremor frequency derived from ultrasound features (e.g., tissue displacement) is equivalent to tremor frequency measured with an accelerometer or electromyography.

Statistical Plan. Primary endpoint is tremor frequency (Hz) per trial/site, summarized as the subject-level mean across trials. For each comparison (US-derived frequency vs accelerometer or EMG), we will test statistical equivalence using TOST with margin  $\Delta=0.5$  Hz by computing the 90% CI of the mean paired difference via a paired t-test; equivalence is concluded if the entire CI lies within  $[-0.5, +0.5]$  Hz (two-sided  $\alpha=0.10$ ). Analyses will be conducted separately by muscle/site (e.g., ECR, FCR) and then pooled across sites; we will report mean differences and 90% CIs along with equivalence conclusions.

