## STATISTICAL DESIGN

### A. Tremor Model Accuracy.

Hypothesis: The data-driven and ultrasound-based tremor prediction model improves wrist angle prediction during tremor compared to the use of accelerometers.

Statistical Plan. Primary endpoint is the patient-level mean NRMSE of wrist angle prediction during tremor, computed by averaging trial NRMSEs within subject. We will perform a within-subject comparison of the data-driven with ultrasound enhanced model versus the accelerometer-only baseline using the Wilcoxon signed-rank test (two-sided  $\alpha=0.05$ ), reporting the Hodges–Lehmann median paired difference and 95% bootstrap CIs; if  $>2$  models are included, we will first run a Friedman test with Holm–Bonferroni-adjusted post-hoc pairwise tests.

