### C. Tremor Suppression

Hypothesis. Afferent stimulation effectively suppresses tremor compared to baseline tremor with no stimulation

Statistical Plan. Primary endpoint is the within-subject tremor suppression ratio, defined as the percent reduction in RMS wrist tremor amplitude during stimulation compared to baseline. Differences across stimulation frequencies will be tested using a one-way repeated-measures ANOVA (within-subject factor: Frequency); if assumptions are not met, the Friedman test will be applied. Upon a significant omnibus result, pairwise frequency comparisons will be performed with Holm–Bonferroni correction, and we will report mean differences with 95% CIs.

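### SAP Section B puts one equivalence hypothesis to about six unadjusted TOST verdicts and does not say which of them, or whether one or all, decides it

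*SAP*

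**What the plan says.** SAP Section B states one hypothesis: frequency from ultrasound features "is equivalent to tremor frequency measured with an accelerometer or electromyography". The testing plan then splits it along two lines.

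- By comparator: "For each comparison (US-derived frequency vs accelerometer or EMG), we will test statistical equivalence using TOST".
- By site: "Analyses will be conducted separately by muscle/site (e.g., ECR, FCR) and then pooled across sites".

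The rule for a single test is clear. A 90% confidence interval for the mean paired difference is computed from a paired t-test, and "equivalence is concluded if the entire CI lies within" the margin of plus or minus 0.5 Hz. For output, "we will report mean differences and 90% CIs along with equivalence conclusions".

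Section B names no deciding comparator, site or pooled result. It has no testing order, no multiplicity adjustment, and no statement of whether one pass or all passes establish the hypothesis. It gives no sample size or SD for these differences.

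The other two sections do mention multiplicity. In Section C, "pairwise frequency comparisons will be performed with Holm–Bonferroni correction" after a significant omnibus test. In Section A, "we will first run a Friedman test with Holm–Bonferroni-adjusted post-hoc pairwise tests", but only if more than two models are included.

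**The concern.** Each test can deliver its own equivalence conclusion under a hypothesis that joins the comparators with the word or. If the results disagree, for example a pass against the accelerometer at one site and a fail against EMG at the other, every single verdict is defined but the verdict on the hypothesis is not. The choice could then be made after the data are seen, and the most favourable result could be taken to support the claim. In that case the 5% error rate of each test is not the error rate of the claim.

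**Working it through.** **1. The plan's own figure.** The SAP gives a 90% CI and two-sided alpha 0.10. TOST at one-sided 0.05 gives 1 − 2 × 0.05 = 0.90 and 2 × 0.05 = 0.10. These agree; the convention is correct for one equivalence test at 5%.

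**2. Number of verdicts.** 2 comparators × (2 example sites + 1 pooled) = 6. The sites are only examples, so six is an illustration.

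**3. Simple bounds if any one pass counts, all true differences at the margin.**
- Upper bound: 6 × 0.05 = 30%.
- Six independent tests: 1 − 0.95^6 = 26.5%.

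Independence cannot hold: the pooled result is built from the site results, and both comparators share the ultrasound signal. Both figures are therefore too high.

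**4. Simulation with dependence.** 20,000 runs per setting, paired-t TOST, every true difference at 0.5 Hz, pooled value taken as the participant's mean over two sites. The SD of paired differences, n and the correlation (the same value between sites and between comparators) are assumptions, because the SAP gives none.

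Chance that at least one of six passes, SD 0.4 Hz:

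| Correlation | n = 12 | n = 20 |
|---|---|---|
| 0 | 21.6% | 20.9% |
| 0.5 | 15.8% | 15.7% |
| 0.7 | 13.4% | 12.9% |

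At correlation 0.9 the rate is about 9–10%, and at 0.95 about 8%.

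With n = 10 and SD 1.0 Hz, where even a single TOST rarely passes:

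| Correlation | Any of six |
|---|---|
| 0 | 14.6% |
| 0.5 | 10.4% |
| 0.8 | 6.9% |
| 0.95 | 4.4% |

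**5. Other decision rules, same true differences** (n = 10, 20, 30; SD 0.3, 0.5, 1.0 Hz; correlations 0 to 0.95):
- One deciding test: 2.0% to 5.2% (the excess over 5% is simulation error).
- Either of the two pooled tests: about 6–10% (about 3–9% at n = 10, SD 1.0 Hz).
- Both pooled tests required: 0.2% to 3.8%.
- All six required: 0% to 2.7%.

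The last two must stay at or below 5%: the chance that all pass cannot exceed the chance that any given one passes.

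**6. How often verdicts split when equivalence is true.** With every true difference at 0.3 Hz, inside the margin, and SD 0.4 Hz, the six verdicts are mixed in 53–90% of trials at n = 12 and 45–77% at n = 20, for correlations 0 to 0.7. Stronger correlation lowers these figures. Under these assumptions a split result is an ordinary outcome.

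**The case against.** The strongest reply is that Section B sets its rule per comparison and promises conclusions in the plural. A natural reading is a set of separately labelled verdicts, each at 5% and all reported, with the word or merely listing two reference instruments. On that reading no single claim exceeds 5%. This stands to the extent that a reader might infer from the wording that a false equivalence claim is far more likely than 5%, and the SAP does not support that. The inference needs a rule that one pass suffices, which the SAP neither adopts nor excludes.

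Other limits also stand:

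- The simulated rates are a worst case, with every true difference exactly on the margin. With all differences at 0.6 Hz, the any-of-six rate at SD 0.4 Hz is only about 0.5% to 2.8%.
- High correlation is plausible, since all the tests share one ultrasound signal and one limb, and it pulls the rate down to about 8%. With small n and large SD it can fall below 5%.
- A reader might count at least six tests, but the sites are examples, so no minimum is documented.
- Sections A and C do not establish a general multiplicity policy from which B departs. Their corrections concern pairwise contrasts, and A's is conditional.

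The objection does not supply the missing rule. There is one hypothesis, and separately labelled verdicts still do not say when it is supported.

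**Conclusion.** The point holds as a gap in the decision rule. Section B leaves open which of about six verdicts, or how many, decides its one hypothesis, so the error rate for that hypothesis is not controlled by the text. If any single pass may support the claim, the false-equivalence rate at the margin is roughly 8% to 22% (SD 0.4 Hz, n = 12 to 20, correlations 0 to 0.95), or about 4% to 15% at n = 10 and SD 1.0 Hz. With one deciding test, or if all must pass, it is at most 5%. SD, n, correlations, two sites and the form of pooling are assumptions. The gap concerns a primary endpoint and should be closed, but it is no evidence that the sponsor intends to claim on the best result. The 90% interval itself needs no change.

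**What to change.** Before analysis, amend Section B to:

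1. Name one deciding test, for example the pooled, participant-level TOST of ultrasound against the accelerometer, and define how sites are pooled within a participant.
2. Test the other comparator, also pooled, only if the first passes, each at one-sided 5%. Alternatively, require both pooled tests to pass.
3. Label site-level results as supportive.
4. Reword the hypothesis to match the chosen rule.

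Nothing in the SAP ranks the accelerometer above EMG, so the order is the sponsor's choice. If the sponsor prefers that any of six may count, each needs 0.05/6, that is, a 1 − 2 × 0.05/6 = 98.33% interval; under independence this gives 1 − (1 − 0.05/6)^6 = 4.9%.

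The cost is SAP wording only, with no change to data collection. A fixed sequence needs no split of alpha. Its downside is that the second comparator cannot be claimed if the first fails; requiring both means that no claim can be made if either fails.

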### C. Tremor Suppression

Hypothesis. Afferent stimulation effectively suppresses tremor compared to baseline tremor with no stimulation

Statistical Plan. Primary endpoint is the within-subject tremor suppression ratio, defined as the percent reduction in RMS wrist tremor amplitude during stimulation compared to baseline. Differences across stimulation frequencies will be tested using a one-way repeated-measures ANOVA (within-subject factor: Frequency); if assumptions are not met, the Friedman test will be applied. Upon a significant omnibus result, pairwise frequency comparisons will be performed with Holm–Bonferroni correction, and we will report mean differences with 95% CIs.

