## **Study Purpose**

The purpose of the study is to use ultrasound imaging to characterize tremor in subjects as they perform grasping motion. In addition, functional electrical stimulation will be applied to study best pathways to suppress tremor.

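### SAP section C hypothesises suppression versus no stimulation, but its planned tests and intervals only compare stimulation frequencies with each other

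*SAP*

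**What the plan says.** The hypothesis in SAP section C, Tremor Suppression, is: "Afferent stimulation effectively suppresses tremor compared to baseline tremor with no stimulation". The primary endpoint is a within-subject suppression ratio, "defined as the percent reduction in RMS wrist tremor amplitude during stimulation compared to baseline". A ratio of 0 therefore means no effect, and a positive ratio means suppression.

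The omnibus analysis is: "Differences across stimulation frequencies will be tested using a one-way repeated-measures ANOVA (within-subject factor: Frequency". The fallback is: "if assumptions are not met, the Friedman test will be applied". The follow-up is: "Upon a significant omnibus result, pairwise frequency comparisons will be performed with Holm–Bonferroni correction, and we will report mean differences with 95% CIs".

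Section C describes no other test or interval. The Protocol describes the two kinds of stimulation but contains no analysis of them.

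Section A, by contrast, tests its hypothesis directly against its own comparator: "within-subject comparison of the data-driven with ultrasound enhanced model versus the accelerometer-only baseline using the Wilcoxon signed-rank test".

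**The concern.** The hypothesis is about the level of the suppression ratio: is it above 0? The planned analysis is about differences in that ratio between frequencies. The two questions can have opposite answers. Stimulation that works equally well at every frequency gives no between-frequency difference to detect. Stimulation that worsens tremor by different amounts at different frequencies gives a clear one.

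Followed as written, the plan would leave one of the SAP's three hypotheses without a matching test. The frequency means would show direction descriptively. Any test against no stimulation would then be chosen after the data are seen, including the choice between an average over frequencies and the best single frequency.

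**Working it through.** There is no figure in section C to reproduce: it gives no sample size, SD, effect size, number of frequencies or alpha. The check has an exact part and an illustrative part.

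**1. What the planned tests can see (exact).** Let Y_if be the suppression ratio of subject i at frequency f, with n subjects and k frequencies. The repeated-measures ANOVA uses

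- MS_freq = n Σ_f (Ȳ_.f − Ȳ..)² / (k − 1)
- MS_error = Σ_i Σ_f (Y_if − Ȳ_i. − Ȳ_.f + Ȳ..)² / [(k − 1)(n − 1)]
- F = MS_freq / MS_error

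Replace every Y_if by Y_if + c. In MS_freq, the two means both rise by c and their difference is unchanged. In MS_error the change is c − c − c + c = 0. The Friedman test uses ranks within subject, which do not move. Each pairwise test and its CI uses Y_if − Y_ig, in which c cancels. So every planned p-value and interval is the same whether mean suppression is −30%, 0 or +30%.

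One simulated data set (n = 12, 4 frequencies) shows this. It was shifted as a whole, and at every shift ANOVA p = 0.000158 and Friedman p = 0.00119.

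| Mean ratio after shift | One-sample t test of subject means against 0, p |
|---|---|
| −30.5 | 0.000043 (worsening) |
| −5.5 | 0.26 |
| +19.5 | 0.0016 (suppression) |

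**2. Size under assumed inputs (illustration).** Assumed, not from the documents: 4 frequencies, residual SD 15 points, between-subject SD 20 points, a normal model, n = 8, 12 or 20, and two-sided alpha 0.05 (the level in section A).

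The ANOVA has 3 and 3(n − 1) degrees of freedom and noncentrality λ = n Σ(μ_f − μ̄)² / 15². The between-subject SD drops out.

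- All frequencies at 40: Σ(μ_f − μ̄)² = 0, so λ = 0 and the rejection rate is alpha.
- 36, 39, 41, 44: the sum is 16 + 1 + 1 + 16 = 34, so λ = 34n/225 = 1.2, 1.8, 3.0.
- −40, −30, −20, −10: the sum is 225 + 25 + 25 + 225 = 500, so λ = 500n/225 = 17.8, 26.7, 44.4.

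For the test of the subject mean against 0, the SD of a subject's mean ratio is √(20² + 15²/4) = √456.25 = 21.4.

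| True ratios | Planned ANOVA rejects, n = 8 / 12 / 20 | Subject mean significantly above 0 |
|---|---|---|
| 40 at every frequency | 5 / 5 / 5% | 99 / 100 / 100% |
| 36, 39, 41, 44 | 12 / 16 / 26% | 99 / 100 / 100% (same mean, 40) |
| −40, −30, −20, −10 | 91 / 99 / 100% | 0 / 0 / 0% |

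Simulation and the noncentral F and t distributions agree on these rates.

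**The case against.** **No stimulation could be a level of the factor.** The SAP lists no levels at all, so a reader could suppose that a 0 Hz condition is one of them. If it were, the shift argument would fail: with a column of zeros added, the omnibus rejects in 99.6% or more of the illustrative trials at 40% suppression, and a pairwise test against that column is exactly a one-sample test against 0. It would not be enough to answer that such a level has no variance. The answer is textual: section C speaks of stimulation frequencies, treats baseline as the reference inside the endpoint, and nowhere names a no-stimulation level. The other reading is possible but less likely, and a plan should not depend on it.

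**The mean differences with CIs could be differences from baseline.** Section C does not define them. As written, they stand in the sentence on pairwise comparisons between frequencies, which opens with the condition of a significant omnibus result. Even on the generous reading, they appear to depend on a test that does not address the hypothesis.

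**Baseline is already in the endpoint.** That is true, and it means the data will exist. It supplies neither a test nor an interval.

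**The percentages rest on invented inputs.** This stands. The 5% figure also needs exactly equal suppression; with near-equal effects the rate is modestly higher. The exact invariance carries the point without them.

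**Conclusion.** The mismatch is real and should be corrected before analysis. As written, no pre-specified test or CI in section C addresses suppression against no stimulation. This rests on the text and on exact algebra. Its numerical size (about 5% rejection under uniform 40% suppression, 91 to 100% when every frequency worsens tremor) holds only under the assumed inputs.

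Two stronger conclusions that a reader might draw are not supported. One is that the study cannot answer its suppression question. It can, because the endpoint requires both baseline and stimulation amplitudes from each subject. The other is that the Protocol's statement of purpose decides between an average effect and an effect at any one frequency. It speaks of pathways, a word that the Protocol's account of stimulation applies to the afferent route, and it does not mention frequencies. The hypothesis itself is silent on the choice, so either is defensible.

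**What to change.** Pre-specify one deciding analysis of the suppression ratio against 0, two-sided at 0.05 with a 95% CI, and not conditional on the between-frequency omnibus. Section C states no alpha; 0.05 follows section A. Conclude suppression only if the result is significant and the estimated ratio is above 0. Choose one route in advance:

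- **(a)** a one-sample t or Wilcoxon signed-rank test (name which) of each subject's mean ratio over the afferent frequencies, with tests by frequency secondary under Holm and unable to rescue a failed overall test; or
- **(b)** a Holm-controlled family of one-sample tests, one per afferent frequency.

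If paired RMS amplitude is also reported, define the difference as baseline minus stimulation and treat it as supportive, since it measures absolute rather than percentage change. Keep the between-frequency ANOVA or Friedman test and its pairwise comparisons as a secondary question.

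The cost is SAP wording only, with no new data. The choice between routes does matter, and it depends on the effect pattern and on a between-subject SD that the documents do not give. Under the same assumptions, with power at n = 8 / 12 / 20:

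| True ratios | Between-subject SD | (a) | (b) |
|---|---|---|---|
| 20 at every frequency | 20 | 62 / 84 / 98% | 49 / 74 / 95% |
| 20 at every frequency | 5 | 100 / 100 / 100% | 97 / 100 / 100% |
| 0, 0, 0, 30 | 20 | 14 / 20 / 32% | 56 / 86 / 99% |
| 0, 0, 0, 30 | 5 | 53 / 75 / 94% | 95 / 100 / 100% |

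For (b), the figure is the chance of finding at least one frequency in the uniform pattern, and of finding the effective one in the other. Running both routes without joint control raises the false-positive rate under a global null to 6.5 to 6.9% (SD 20) or 8.3 to 8.9% (SD 5). The choice should therefore be fixed before the data are seen.
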